- Change from baseline in spleen size (in subset of patients with no prior-splenectomy)

The **exploratory endpoints** will include evaluation of biomarkers related to the TGF- β superfamily, quality of life, change in spleen size (in subset of patients with no prior splenectomy), change in BMD, change in EMH mass size, change in leg ulcer size, and change in the 6MWT distance in NTD patients.

All binary endpoints will be summarized using both a point estimate and its exact confidence interval based on the binomial distribution. The time-to-event type secondary endpoints will be analyzed using Kaplan-Meier method to estimate the survival curve and median time to event and 95% confidence interval.

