3.3. Rollover to Extension Study

Consenting patients that meet the A536-06 eligibility criteria may immediately roll over from A536-04 to study A536-06 following the last ACE-536 dose. These patients may forego the End of Study (EOS) visit in study A536-04 to begin study A536-06.

Patients who complete the EOS visit for study A536-04 and are \geq 28 days post EOS visit may also roll over to study A536-06. These patients will be re-assessed for eligibility by meeting all eligibility criteria plus additional inclusion criteria for study A536-06.

Patients who do not meet the above criteria (e.g., $>$ 35 days after last dose in study A536-04 and $<$ 28 days post EOS visit in study A536-04) may still participate, but should not begin study A536-06 C1D1 until they have reached \geq 28 days post EOS visit from study A536-04.

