3.4. Sample Size

There was no formal sample size calculation for the dose escalation portion of the study. A sample size of 30 evaluable patients in the expansion cohort will provide approximately 87% power with 1-sided significance level of 0.05 to differentiate an erythroid response rate of 30% from a minimal erythroid response rate of 10%.

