5.7. Efficacy Analyses

All efficacy endpoint will be performed using the ITT population.

All efficacy summaries will be presented by dose cohort and for NTD and TD patients separately. In addition, the dose cohorts will be combined and presented as low dose group and high dose group. Low dose group includes patients on 0.2 and 0.4 mg/kg dose cohorts. High dose group includes patients on 0.6 mg/kg and above. No formal hypothesis testing is planned.

In general, below rules apply to the derivations of efficacy endpoints which utilize hemoglobin and RBC transfusion data unless specified otherwise:

- Hemoglobin measurements within 14 days following RBC transfusion will be excluded from efficacy analysis
- For each patient, all efficacy endpoints will be derived based on an analysis cut-off day, defined as the last dose + 56 days or the last date from transfusion record data, whichever is earlier.

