5.7.2.2. Time to and Duration of Erythroid Response

Time to and duration of erythroid response will be analyzed for erythroid responders defined as below:

- For NTD patients, mean increase of ≥ 1.0 g/dL from pretreatment hemoglobin during any rolling 12 weeks
- For TD patients, $\geq 50\%$ reduction in RBC transfusion burden compared to pretreatment using 12-week intervals.

Time to erythroid response will be defined as the time from the first dose date to the first date of any rolling 12-week window achieving above erythroid response.

Duration of erythroid response will be defined as the time from the starting date of the first rolling 12-week window achieving response to the last date of the consecutive rolling 12-week window achieving response. When there are multiple disjoint intervals with response, the longest interval will be used. Patients with response ongoing by the analysis cutoff day will be censored.

Both time to and duration of erythroid response will be analyzed as continuous variables and summarized by descriptive statistics. In addition, duration of erythroid response will also be analyzed as a time to event endpoint.

The derivations of time to and duration of erythroid response will be listed for each patient.

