- ¹⁰ **Pregnancy** test (urine or serum) and menstrual history is required prior to C1D1 for female patients of child bearing potential only.
- ¹¹ Transfusion history will be collected for 12 months prior to C1D1.
- ¹² **End of Treatment (EOT):** Should be performed 28 days (± 7 days) after the last dose of ACE-536. Patients who discontinue treatment early should complete the end of treatment visit at the time of discontinuation and complete the Day 141 follow up visit 28 days (± 7 days) after the EOT visit.
- ¹³ **End of Study (EOS):** Should be performed 28 days (± 7 days) after the Day 113/EOT visit (56 days after the last dose of ACE-536).
- ¹⁴ **Day 85 ± 2 days** is the last possible study day that ACE-536 may be administered, regardless of the cycle.
- ¹⁵ If a **dose delay** is required per the dose modification rules the patient will not be dosed. The patient will return weekly to assess hematology results and adverse events until the patient is eligible to administer the next dose of ACE-536.
- ¹⁶ If the patient has a positive ADA result at their last assessment, the patient may be asked to return approximately every three months for additional testing until a negative result is obtained or the result is considered stabilized.
- ¹⁷ MRI for liver iron content will be performed at selected sites.
- ¹⁸ For the first dose of ACE-536, dosing should occur after a minimum of 7 days post-transfusion; subsequent doses should not be given within 24 hours of transfusion or planned transfusion.
- ¹⁹ Administration of quality of life questionnaires, including but not limited to FACT-An and SF-36 is required for patients in the expansion cohort only.
- ²⁰ QoL questionnaires including but not limited to FACT-An and SF-36 should be completed at the EOT visit only for expansion cohort patients who discontinue treatment early.
- ²¹ Abdominal ultrasound of the spleen is required for patients with no prior splenectomy in the dose escalation cohorts only. Patients in these cohorts with clinical signs of a change in spleen size or abnormality should have an abdominal ultrasound as needed throughout study.
- ²² Pregnancy test is not required at Day 141/EOS.
- ²³ Physical exam should include an optional evaluation of gonadal size in males at C1D1, EOT, and EOS visits only.
- ²⁴ MRI of the chest and abdomen for EMH masses and spleen, DXA for BMD and 6MWT for NTD patients will be performed in the expansion cohort patients only, at selected sites.

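### Duration of response is summarised with censored values counted as complete, so long responses are understated; separately, the protocol's Kaplan-Meier analysis of time to response becomes a responders-only summary without being listed as a change

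*SAP*

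**What the plan says.** SAP 5.7.2.2 restricts both endpoints to responders: a mean hemoglobin rise of at least 1.0 g/dL over a rolling 12 weeks (NTD), or at least a 50% fall in transfusion burden over 12 weeks (TD). Time to response runs from first dose to the start of the first responding window. Duration runs from that start to the end of the last consecutive responding window.

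On censoring it says: "Patients with response ongoing by the analysis cutoff day will be censored". It continues: "Both time to and duration of erythroid response will be analyzed as continuous variables and summarized by descriptive statistics". The next sentence adds a time-to-event analysis, for duration only. SAP 5.2 provides Kaplan-Meier curves when there are more than 5 patients.

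Follow-up is short. The SAP schedule of events says that Day 85 (± 2 days) "is the last possible study day that ACE-536 may be administered, regardless of the cycle". SAP 5.7 sets the analysis cut-off, "defined as the last dose + 56 days or the last date from transfusion record data, whichever is earlier". SAP 3.3 says of patients entering the extension: "These patients may forego the End of Study (EOS) visit in study A536-04 to begin study A536-06".

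Protocol 15.2.3 lists both time to and duration of erythroid response as secondary analyses in the ITT and EE populations, and says: "The time-to-event type secondary endpoints will be analyzed using Kaplan-Meier method to estimate the survival curve and median time to event", with a 95% confidence interval. SAP 5.13 lists two changes from the protocol, the baseline hemoglobin definition and removal of the EE population.

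**The concern.** A censored duration is a lower bound. Averaging it with completed durations treats the day observation stopped as the day the response ended. The mean is then biased low, and so is the median once censoring is heavy. A durable response is what a reader would most want to see here, and it is the case in which the summary fails.

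Time to response raises a different issue. Every responder's start day is observed, so the responders-only summary contains no censored values. It is conditional on having responded, however, and non-responders contribute nothing. The protocol assigned Kaplan-Meier to this kind of endpoint, and Protocol 15.5 says deviations from its analyses will be indicated in the SAP.

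**Working it through.** **The plan's own figure.** The only design figure is in SAP 3.4: "A sample size of 30 evaluable patients in the expansion cohort will provide approximately 87% power with 1-sided significance level of 0.05", for 30% against 10%. A continuity-corrected normal approximation reproduces it: Φ{[(0.20 − 1/60)√30 − 1.645 × √(0.1 × 0.9)] / √(0.3 × 0.7)} = 86.7%. It has no bearing on duration. The documents give no figure for duration, so the sizes below rest on assumptions.

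**Possible range of recorded durations.**
- Cut-off: 85 + 56 = Day 141.
- Shortest duration: one 12-week window, 84 days.
- Latest start of a full window: 141 − 83 = Day 58.
- Longest duration for a start on day S: 141 − S + 1, so 141 days for a Day 1 start and 84 for a Day 58 start.
- If a rollover patient's record ends 35 or 28 days after the last dose (assumed), the cut-off is Day 120 or 113 and the range is 84–120 or 84–113 days.

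**Naive mean, Day 1 start.** Assume a true duration of 84 days plus an exponential time with median w weeks, so λ = ln 2 / (7w). The room beyond 84 days is 141 − 84 = 57 days.
- Share censored: exp(−57λ)
- Naive mean: 84 + [1 − exp(−57λ)] / λ
- True median: 84 + 7w
- True mean: 84 + 1/λ

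| w (weeks beyond Day 84) | True median | True mean | Censored | Naive mean |
|---|---|---|---|---|
| 1 | 91 | 94 | 0.4% | 94 |
| 2 | 98 | 104 | 6% | 103 |
| 4 | 112 | 124 | 24% | 115 |
| 12 | 168 | 205 | 62.5% | 129.5 |
| 26 | 266 | 347 | 80.5% | 135.2 |
| 52 | 448 | 609 | 89.7% | 138.0 |

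In the last three rows more than half are censored, all at 141 days, so the naive median is 141 days in each.

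**Later starts.** Averaging the same formula over start days, with 57 replaced by 58 − S, for w = 12, 26 and 52:
- Starts uniform over Days 1–22: naive means 122.5, 126.6 and 128.5 days.
- Starts uniform over Days 1–58: naive means 108.5, 110.5 and 111.5 days.

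The plateau therefore depends on when responses start and lies well below 141 when starts are late.

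**Kaplan-Meier on the same kind of data.** In a simulation of 20,000 responders (same form of duration, Day 141 cut-off, both ranges of start days), the Kaplan-Meier median was 88, 95 and 109 days for true medians of 88, 95 and about 109. It was not reached once the true median was about 142 days or more, which is the correct report.

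**Where the time-to-event analysis may not appear.** SAP 3.1 shows five escalation cohorts of 6 patients and one of 5. SAP 5.7 presents efficacy by cohort and for NTD and TD separately, and 5.7.2.2 keeps responders only. More than 5 patients in such a cell would need all 6 in a cohort to be of one type and to respond. Curves are realistic mainly for the expansion cohort and the pooled dose groups.

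**The case against.** The strongest reply is that a valid analysis of duration is already planned. The sentence after the quoted one provides it, the censoring rule is stated, and each patient's derivation is listed. This stands. A reader might infer that the SAP offers only a biased duration analysis; it does not. The reply is weaker in the small cohorts, where the curve threshold leaves the descriptive summary exposed, and the SAP does not restate the protocol's median and confidence interval.

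A reader might also infer that the descriptive duration is pinned near the end of follow-up whatever the truth. The documents do not support that. Responses ending before the cut-off are recorded in full, and the first three rows of the table show the summary following them closely. A 12-week response would be recorded as about 84 days. The loss of sensitivity is confined to long responses: the w = 12 and w = 52 rows are total durations of 24 and 64 weeks at the median.

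On time to response, the SAP does account for non-responders elsewhere: 5.7.2.1 reports proportions, with exact intervals, for the same two response definitions in the ITT population. With nearly complete follow-up, a Kaplan-Meier curve would largely recombine those rates with the start days. SAP 5.13 also claims to list only major changes. Both points lower the consequence; neither explains replacing a named method without comment. Nor does the protocol say that non-responders are to be censored at the cut-off. It names the method and the populations only.

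Finally, all summaries are descriptive, no formal test is planned, and no decision rule uses this table.

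**Conclusion.** The point holds in limited form. Followed as written, the descriptive duration counts censored values as complete. It tracks short responses and understates long ones: under the assumed model, true means of about 205, 347 and 609 days give naive means of 130, 135 and 138 with Day 1 starts, and 108.5 to 128.5 days with later starts. The exponential form, its medians and the start days are assumptions; the range of about 84 to 141 days follows from the SAP's own rules for a patient last dosed on Day 85.

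The move from Kaplan-Meier to a responders-only summary of time to response is a separate, unlisted departure from the protocol. It does not affect duration. Severity is minor to moderate, because these are descriptive secondary endpoints and duration also has a time-to-event analysis.

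**What to change.** In SAP 5.7.2.2:
- Make Kaplan-Meier the main summary of duration: median (or not reached), 95% confidence interval and number censored.
- Drop the descriptive mean and median of duration, or label them as observed duration including censored values, with the number censored shown and censored values marked. Labelling suffices, and it keeps something in the small cohorts.
- Restore Kaplan-Meier, or cumulative incidence, for time to response in all ITT patients, with non-responders censored at the cut-off. The SAP must add that rule. Keep the responders-only summary as supplementary.
- If time to response is not restored, list and justify the change in SAP 5.13.

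The cost is SAP wording and one further output. The time-to-event analysis of duration is already planned, and no new data are needed.

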5.7.2.3. Iron Parameter Related Analysis

Iron metabolism parameters including serum iron, total iron binding capacity (TIBC), transferrin, soluble transferrin receptor, ferritin, non-transferrin bound iron (NTBI), and hepcidin will be taken at Screening, Day 1, 8, and 15 of Cycles 1, Day 1 of Cycle 2, 3, 4, 5, EOT and EOS visits. Descriptive statistics of actual values, absolute and percentage change from baseline values at each postbaseline time point will be presented by dose cohort. The summary will also be provided by NTD and TD.

MRI for Liver Iron Content (LIC) will be performed at baseline and EOT. Descriptive statistics of actual values, absolute and percentage change from baseline at EOT visit will be presented by dose cohort. The summary will be done by NTD/TD and baseline LIC ≥ 3 and < 3 mg/g dw subgroups separately.

LIC response will be defined as LIC reduction ≥ 1 mg/g dw at EOT compared with baseline, for patients with baseline LIC ≥ 3 mg/g dw only. LIC response rate along with the exact 95% confidence interval will be estimated for NTD and TD patients respectively, as well as by baseline ICT use (yes vs no).

Shift analyses will also be performed to summarize serum ferritin EOT change from baseline. Serum ferritin will be grouped into three categories: < 300 , ≥ 300 and ≤ 1000 , ≥ 1000 ($\mu\text{g/L}$).

Plots of iron parameters for both mean observed values and mean change from baseline over time will be presented by dose cohort.

5.7.2.4. Erythropoiesis Parameters

Blood samples relating to erythropoiesis parameters include serum erythropoietin (EPO) levels, hemoglobin electrophoresis, globin chain RNA, reticulocytes and nucleated RBCs. EPO will be taken at Screening, Day 1 of Cycles 1, 2, 4, EOT, and EOS. Hemoglobin electrophoresis and globin chain RNA will be taken at C1D1, C4D1 and EOT. Reticulocytes

and nucleated RBCs will be taken at Screening, Day 1, 8, and 15 of Cycles 1, 2, 3, 4, 5, EOT and EOS visits. Descriptive statistics of observed values, absolute and percentage change from baseline values at each postbaseline visit will be presented by dose cohort and for TD and NTD separately. Plots of erythropoiesis parameters for both mean observed values and mean percentage change from baseline over time will be presented by dose cohort.

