5. STATISTICAL METHODOLOGY

5.1. Definitions

Transfusion Dependent (TD)

Based on protocol, TD patients are defined as those who required ≥ 4 units of RBCs every 8 weeks (confirmed over 6 months prior to Cycle 1 Day 1).

For programming implementation, a patient is defined as TD if the total RBCs is ≥ 11 units during 26 weeks on or prior to Cycle 1 Day 1.

Non-Transfusion dependent (NTD)

NTD patients are those who do not meet the above definition for TD. For programming implementation, NTD patients are defined as those who received < 11 units of RBCs during 26 weeks on or prior to Cycle 1 Day 1.

Baseline Hemoglobin

Baseline hemoglobin will be an average of hemoglobin measurements within 28 days of Cycle 1 Day 1, excluding measurements within 14 days following RBC transfusion.

Baseline Transfusion Burden

Baseline transfusion burden will be calculated as the total amount of RBC transfusions during the 12 weeks on or prior to Cycle 1 day 1.

Baseline for Other Parameters

Baseline erythropoietin (EPO) is defined as the maximum test value within 28 days of Cycle 1 Day 1. For all other parameters, baseline is defined as the last observation on or prior to Cycle 1 Day 1.

Transfusion Unit Conversion

The transfusion amount measured in unit “mL” will be converted to “units” according to medical review.

End of Treatment (EOT)

Procedures and evaluations for the end of treatment visit should be performed 28 days (± 7 days) after the last dose of ACE-536.

End of Study (EOS)

Procedures and evaluations for the end of study visit should be performed 28 days (± 7 days) after the Day 113/EOT visit (56 days after the last dose of ACE-536).

Combined Dose Groups

Low dose group includes patients on 0.2mg/kg and 0.4 mg/kg dose cohorts. High dose group include patients with dose level 0.6 mg/kg and above. Suitable summaries may be presented by low/high dose as specified.

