5.2. General Considerations

Unless otherwise noted, continuous data will be summarized with the following descriptive statistics: number of observations (n), mean, standard deviation (STD), minimum, median, and maximum. Categorical data will be summarized with frequencies (n) and percentages (%). In cases where missing data cause percentages not to sum to 100, a missing data row will be

provided. Percentages will use column totals as the denominator unless otherwise indicated. For time to event variables, the Kaplan-Meir curves will be presented if the number of patients is more than 5.

All study data will be included in study data listings. Missing data will generally be treated as missing, not imputed, unless otherwise stated.

All summaries will be presented by dose cohort, and may also be presented by low/high dose groups as specified. The summaries may also be presented for TD and NTD patients separately as specified. All summaries will be descriptive. No formal hypothesis testing is planned.

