5.7.2.6. Hemolysis Parameters

Hemolysis parameters include haptoglobin, indirect bilirubin, and lactate dehydrogenase (LDH). Haptoglobin will be taken at Screening, Day 1, 8, and 15 of Cycles 1, 2, 3, 4, 5, EOT and EOS visits. Indirect bilirubin and LDH will be taken at Screening, Day 1 and 15 of Cycle 1, Day 1 of Cycles 2, 3, 4, 5, EOT and EOS visits. Descriptive statistics of observed values, absolute and percentage change from baseline values at each postbaseline visit will be presented by dose cohort. Plots of hemolysis parameters for both mean observed values and mean percentage change from baseline over time will be presented by dose cohort and for TD and NTD separately.

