5.9.5. Statistical Analysis

All ACE-536 serum concentrations will be listed by dose group, subject, and scheduled time (visit and study day). The ACE-536 serum concentrations will be summarized by dose group and scheduled time, including N (number of observations), arithmetic mean, arithmetic standard deviation (SD), arithmetic coefficient of variation (CV%), geometric mean, geometric CV%, minimum, median, and maximum. Mean (SD) serum concentration-time profiles will be presented on both linear and semilogarithmic scales by dose group for the first 4 weeks. Individual concentration plots will be provided by presenting the observed concentration data along with the one-compartment model-predicted concentration-time profile on the linear scale using actual sampling times and multiple dose data.

Pharmacokinetic parameters will be listed by dose group and subject, and they will be summarized descriptively by dose group (N, mean, SD, minimum, median, maximum, CV%, geometric mean, and geometric CV%). Dose proportionality may be assessed using the exposure data (e.g., C_{max}, AUC) after the first dose. The relationship between ACE-536 exposure and response (i.e., safety, efficacy, and biomarkers) may be explored, if appropriate.

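### The erythropoiesis and hemolysis plots show arithmetic mean percentage change, which drifts upward with within-patient noise; a geometric mean ratio would be a better summary (minor)

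*SAP*

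**What the plan says.** SAP 5.7.2.4 covers erythropoietin (EPO), hemoglobin electrophoresis, globin chain RNA, reticulocytes and nucleated red cells. Its plots are specified as follows: "Plots of erythropoiesis parameters for both mean observed values and mean percentage change from baseline over time will be presented by dose cohort". SAP 5.7.2.6 covers haptoglobin, indirect bilirubin and LDH, and its plots likewise show "mean percentage change from baseline over time will be presented by dose cohort and for TD and NTD separately".

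The tables are broader than the plots. SAP 5.7.2.4 specifies "Descriptive statistics of observed values, absolute and percentage change from baseline values at each postbaseline visit will be presented by dose cohort and for TD", with non-transfusion-dependent patients shown likewise. SAP 5.7.2.3 does much the same for iron parameters: "absolute and percentage change from baseline values at each postbaseline time point will be presented by dose cohort". Sections 5.7.2.5 (bone markers) and 5.7.3.1 (GDF8, GDF11, GDF15) also tabulate observed values, change and percentage change, with no plots. SAP 5.2 sets the default content of a continuous summary as "number of observations (n), mean, standard deviation (STD), minimum, median, and maximum".

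The baseline rule differs by marker. For EPO, SAP 5.1 says: "Baseline erythropoietin (EPO) is defined as the maximum test value within 28 days of Cycle 1 Day 1". Hemoglobin has its own averaged baseline. Every other marker uses one value, the latest one obtained up to the first dosing day.

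No log-scale summary is planned for any biomarker. The PK section (SAP 5.9.5) does list "geometric mean, geometric CV"% alongside the arithmetic statistics.

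**The concern.** A percentage change is a ratio to an observed baseline, and ratios are asymmetric: a patient whose value doubles contributes +100%, while one whose value halves contributes only -50%. If the baseline is a single noisy measurement, patients who happen to read low at baseline pull the arithmetic mean up by more than those who read high pull it down. The mean percentage change is then expected to be above zero even if nothing has happened.

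Change in biomarkers of erythropoiesis and hemolysis is a stated secondary objective. The study is open-label with no concurrent control, so no comparator curve would reveal the drift. The escalation cohorts have 5 or 6 patients (SAP 3.1) and are split further into TD and NTD, so a plotted curve can rest on very few ratios. A fall in LDH or indirect bilirubin could be understated, or a rise in reticulocytes overstated.

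**Working it through.** **Figures in the plan.** The plan gives no figure for the biomarkers: no SD, no CV and no target change. Its one design figure, about 87% power for the primary endpoint, is not involved. The within-patient CV below is therefore an assumption, shown as a range.

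**Single-value baseline.** Let X be the baseline and Y the later value for the same patient, with independent lognormal within-patient error of log-variance s², where s² = ln(1 + CV²). If the true ratio is R, then

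E[Y/X] - 1 = R·exp(s²) - 1 = R(1 + CV²) - 1.

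The patient's own level cancels, so spread between patients plays no part.

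| Assumed within-patient CV | No change: 1 × (1 + CV²) - 1 | True 20% fall: 0.8 × (1 + CV²) - 1 | Median % change, no change |
|---|---|---|---|
| 10% | +1% | -19.2% | 0% |
| 20% | +4% | -16.8% | 0% |
| 30% | +9% | -12.8% | 0% |
| 50% | +25% | 0.0% | 0% |

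Simulation with 2 million draws per row agreed with the no-change column.

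**Is it skew, or within-patient noise?** With between-patient log-SD from 0.3 to 1.5, the drift was 0% when within-patient variation was nil and about +4% at CV 20%. Symmetric normal error at CV 20% gave about +4.6%. The cause is noise in the denominator, not a skewed marker.

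**Drift against sampling noise.** With no change, the SD of one patient's percentage change is √[exp(2s²)(exp(2s²) - 1)]. At CV 30% this is about 47 points, so the standard error is 47/√6 ≈ 19 points in a cohort of 6 and 47/√30 ≈ 9 points in the expansion cohort. At CV 50% it is about 94 points, giving 38 and 17. The drift does not shrink with n.

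**Does the geometric mean ratio do better?** Its expected log ratio is ln R exactly, with standard error s√(2/n). Take n = 6 and a true 20% fall (ln 0.8 = -0.223). The chance that the cohort summary points the wrong way (above zero) is:

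- CV 30% (s = 0.294): geometric ratio Φ(-0.223/0.169) = 9%; mean percentage change 19% by simulation.
- CV 50% (s = 0.472): geometric ratio Φ(-0.223/0.273) = 21%; mean percentage change 44% by simulation.

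**EPO.** Two pre-dose values are scheduled (Screening and Cycle 1 Day 1), and baseline is the larger. With no change,

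E[Y/max(X₁, X₂)] - 1 = 2·exp(s²)·Φ(-s/√2) - 1.

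- CV 20%: 2 × 1.04 × 0.4443 - 1 = -7.6%
- CV 30%: 2 × 1.09 × 0.4178 - 1 = -8.9%
- CV 50%: 2 × 1.25 × 0.3692 - 1 = -7.7%

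The sign turns positive only above a CV of about 76%. A geometric ratio does not cure this. The expected maximum of two normal log values lies s/√π above their mean, so the ratio is expected at exp(-s/√π) - 1, which is -11%, -15% and -23% at the same CVs.

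**The case against.** The strongest reply is that little depends on these plots. SAP 5.2 says: "All summaries will be descriptive. No formal hypothesis testing is planned". The same section puts the median, minimum and maximum in the default summary, and the median percentage change is free of this drift for a single-value baseline. Absolute change is tabulated too. The iron plots use mean change, not percentage change. Bone markers and GDFs are not plotted, ferritin also has a shift analysis, and all data are listed. At CV 10% the drift is 1 point, and at CV 30% it is no larger than the standard error. All of this stands, and it is why the point is minor. It does not rescue the two sets of plots, which show means only, and the drift does not average out as n grows.

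A reader might also infer more than the documents support:

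- *That the biomarker results will be wrong.* The size depends on a CV that the documents do not give. The plots can mislead; nothing shows that they will.
- *That skewed markers are the cause.* The documents do not describe the markers as skewed, and between-patient skew does not produce the drift.
- *That EPO is inflated as well.* Its maximum-value baseline pushes it the other way over any CV up to about 76%.
- *That dose comparisons are distorted.* With a common CV, the factor (1 + CV²) is the same in every cohort, so it creates no dose trend. Noise in small cohorts affects any summary.
- *That the PK section is a precedent for dropping arithmetic means.* It reports arithmetic and geometric statistics side by side. It shows only that the method is already in the plan.

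**Conclusion.** The point holds as a minor improvement to presentation. For markers with a single-value baseline, the mean percentage change plotted under SAP 5.7.2.4 and 5.7.2.6 overstates the true change by R × CV², where R is the true ratio: +1, +4, +9 and +25 points with no change at assumed within-patient CVs of 10, 20, 30 and 50%. This assumes independent lognormal error; symmetric error at CV 20% gives a similar figure. The geometric mean ratio removes the drift and, at n = 6, roughly halves the chance that a true 20% fall is displayed as a rise.

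EPO falls outside this conclusion. Its baseline definition gives an expected fall of about 8 to 9% with no effect at CVs of 20 to 50%, and that needs its own correction. The primary endpoint and its power are unaffected.

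**What to change.** 1. In the plots of SAP 5.7.2.4 and 5.7.2.6, for strictly positive markers with a single-value baseline (such as reticulocytes, LDH and indirect bilirubin), replace mean percentage change with the geometric mean ratio to baseline, expressed as 100 × (exp(mean log ratio) - 1), with a 95% confidence interval.
2. Add the same statistic to the percentage-change tables in 5.7.2.3 to 5.7.2.6 and 5.7.3.1, keeping the summaries already planned.
3. Where zeros can occur, such as nucleated red cells, plot the median absolute change. Percentage change is undefined at a zero baseline, and neither SAP 5.2 nor 5.12 gives a rule for it.
4. For EPO, define baseline for change as the last or the average pre-dose value (averaged on the log scale if the ratio is used).

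The cost is programming and a short SAP revision, with no new data. The downside of items 1 to 3 is the exception for zeros. For item 4, baseline EPO also defines subgroups in SAP 5.7.4, so the SAP should say whether the new definition applies there or only to change from baseline.
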